6.1.3 Visit 3 (Day 4)

The assessments listed below will be conducted. See [Table 2](#) for details for efficacy assessments and blood collections for █ BDNF.

- Administer safety assessments (C-SSRS [Since Last Visit Version])
- Review AEs
- Review concomitant medications
- Administer SM
- Administer efficacy assessments following SM administration (HAM-D₆ and MADRS)
■ [REDACTED]
■ [REDACTED]
- Collect blood sample for BDNF concentration following SM administration (after efficacy assessments)
- Review ADT adherence diary

6.1.4 Visit 4 (Day 7)

The assessments listed below will be conducted. See [Table 2](#) for details for efficacy assessments and blood collections for [REDACTED] BDNF.

- Record body weight
- Record vital signs (orthostatic blood pressure and pulse rate, respiratory rate, and oral temperature)
- Perform 12-lead ECG
- Collect blood samples for:
 - Hematology and serum chemistry (non-fasted sample allowed)
 - BDNF pre-dose
■ [REDACTED]
- Collect urine sample for:
 - Urine pregnancy test (FOCP only)
 - Urinalysis
 - Drug and alcohol screen
- Administer efficacy assessments (pre-dose HAM-D₆, MADRS, and CGI-S)
- Administer safety assessments (C-SSRS [Since Last Visit Version], CADSS, and BPRS+ scales)
- Review AEs
- Review concomitant medications
- Administer SM
- Administer efficacy assessments following SM administration (HAM-D₆ and MADRS)
■ [REDACTED]
■ [REDACTED]
- Collect blood sample for BDNF concentration following SM administration (after

efficacy assessments)

- Review ADT adherence diary

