The evaluation period includes 4 clinic visits (on days 1, 4, 7 and 10). Subjects will receive SM at the clinic on days 1, 4 and 7. Subjects will not receive SM on days 2, 3, 5, 6, 8, 9 and 10. Subjects will continue their ADT throughout the study. All safety, efficacy, , and pharmacodynamic (PD) assessments and procedures will be performed as outlined in [Table 1](#) and [Table 2](#).

At the end of study (EOS; Day 10) or early termination (ET), if applicable, subjects will return to the clinic for the EOS visit. Approximately 5 days (+2 days) after the last administration of SM (Day 7) and once all study visits are completed; subjects will receive a safety follow-up phone call. Subjects who discontinue the study due to adverse events (AEs) will be followed for at least 30 days following the date of last administration of SM or until resolution, or until, in the medical judgment of the investigator, the event has stabilized or is assessed as chronic.

Duration of Subjects' Participation:

The total study duration for each subject's participation is up to 40 days (screening period [up to 28 days], evaluation period [10 days], and safety follow-up phone call [5 days from Day 7]).

Investigational Medicinal Products, Reference Therapy, Doses and Mode of Administration:

Study Medication: SPN-820 400 mg capsules

Dosage: 2400 mg (six 400-mg capsules) administered once a day every 3 days

Mode of Administration: Oral, as intact capsules, in the morning approximately 3 hours after breakfast

Sampling for [REDACTED] Pharmacodynamic Assessments:

[REDACTED]
[REDACTED]
[REDACTED].

Seven total blood samples will be collected for measurement of BDNF concentrations: 3 pre-dose collections on days 1, 4, and 7; 3 post-dose collections 4 hours after SM administration on days 1, 4, and 7; and 1 collection on Day 10.

Statistical Methodology:

Sample Size: Approximately 50 subjects will be enrolled to achieve approximately 40 subjects completed. This sample size is based on clinical judgment without a power calculation.

Analysis Populations:

The full analysis set (FAS) includes all subjects who receive at least one dose of SM and have a baseline and at least one post-baseline measurement of HAM-D₆.

The safety population includes all subjects who receive at least one dose of SM.

[REDACTED]
[REDACTED].

The PD population includes subjects who receive at least one dose of SM and have a baseline and at least one post-baseline BDNF concentration.

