2.4 Clinical Studies

[figure not shown]
The PK, pharmacodynamics (PD), preliminary efficacy, and safety of SPN-820 have been evaluated in 6 completed Phase 1 clinical studies.

Completed Studies

A total of 145 adult subjects have been exposed to SPN-820 in the Phase 1 studies, including 129 healthy subjects and 16 subjects with TRD. Single doses up to 2400 mg and multiple doses up to 3000 mg for 7 days have been administered in the Phase 1 clinical studies.

- Study NAV-17A-001 was a Phase 1a/1b, randomized, two-part, double-blind, placebo-controlled, on-site study of single ascending dosage levels of SPN-820 or placebo in 48 healthy subjects (Part A) and a single dose of SPN-820 2400 mg or placebo in 32 subjects with TRD (Part B).
- Study NAV-17A-002 was a Phase 1, randomized, double-blind, placebo-controlled, on-site, single-dose study to evaluate the safety, PK, metabolomic and proteomic profiles of SPN-820 in plasma and cerebrospinal fluid (CSF) in healthy male subjects between the ages of 18 and 55 years.
- Study NAV-17A-003 was a randomized, double-blind, placebo-controlled, on-site study of the effects on quantitative electroencephalography and event-related potential of 2 sequential doses of SPN-820 or placebo administered 48 hours apart, to healthy adult male subjects.
- Study NAV-17A-004 was a Phase 1, randomized, double-blind, placebo-controlled, single-center study of the safety, tolerability, and PK of multiple ascending doses of SPN-820 in healthy subjects.
- Study NAV-17A-005 was a Phase 1, 4-period, 4-treatment, 4-sequence crossover study in which subjects received a single dose of SPN-820 400 mg oral solution, 400 mg capsule, 1600 mg oral solution, and 1600 mg capsule under fasted conditions.
- Study NAV-17A-006 was a Phase 1, open-label, single-dose, mass balance study to assess the disposition of [14C]-SPN-820 in healthy male subjects.

Completed Study Results

[figure not shown]

Safety

The majority of treatment-emergent adverse events (TEAEs) reported by healthy subjects were reported as mild, none were severe, and all resolved. The most frequently reported TEAEs by healthy subjects included dizziness (postural dizziness and orthostatic hypotension) nausea, headache, and somnolence. Two subjects who received single doses of SPN-820 400 mg discontinued due to adverse events (AEs): muscle strain, nausea, and vomiting (n=1); vomiting (n=1).

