3.2.4 Safety Endpoints

- TEAEs.
- Clinical safety laboratory test results.
- Vital sign measurements including orthostatic blood pressure and pulse rate.

- Body weight.
- Electrocardiography (ECG) findings.
- Physical examination findings.
- Suicidal ideation and behavior as measured by the Columbia Suicide Severity Rating Scale (C-SSRS) score.
- Dissociative symptomatology as measured by the Clinician-Administered Dissociative State Scale (CADSS) score.
- Psychopathology severity as measured by the Brief Psychiatric Rating Scale Positive Subscale (BPRS+) score.

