6 STUDY METHODS

The Schedule of Events and Assessments is provided in [Table 1](#), and a detailed schedule of timed assessments (Window) is provided in [Table 2](#).

All subjects who are enrolled and receive the initial administration of SM on Day 1 will be followed according to the protocol regardless of the number of doses of SM taken, unless consent for follow-up is withdrawn. The Sponsor or Sponsor's designee must be notified of all deviations from the protocol clinic visits or procedures, except as noted, and these procedures, if applicable, will be rescheduled or performed at the nearest possible time to the original schedule. AEs should be reported during clinic visits and during at-home contacts. Subjects will also be instructed to call study personnel to report any AEs during the intervals outside the established study contacts and to come to the clinic/or seek medical care if medical evaluation is needed and as the urgency of the situation indicates. For emergencies and other unscheduled visits to a medical facility other than the clinic, medical records will be obtained by the investigator or qualified designee as source data for study follow-up.

Table 1: Schedule of Events and Assessments

Study Period	Screening	Evaluation Period							Safety/ Follow-Up (FPC ^a)
		Seven-Day Treatment Period						EOS/ ET	
	Clinic	Clinic (Baseline)	Home	Clinic	Home	Clinic	Home	Clinic	Home
Visit Number	1	2	-	3	-	4	-	5	
Study Day	-28 to -1	1	2-3	4	5-6	7	8-9	10	12
Window Visit (days)									+2
Sign informed consent	X								
Review eligibility criteria	X	X							
Demographics	X								
Medical history ^b	X								
Confirm MDD diagnosis	X								
Record prior medications	X								
Confirm stable, therapeutic dose of one study-approved ADT	X								
MINI	X								
Physical examination ^c	X	X						X	
Height	X								
Body weight	X	X		X		X		X	
Calculation of body mass index	X								
Vital signs with orthostatic blood pressure and pulse rate ^d	X	X		X		X		X	
12-Lead ECG ^e	X	X		X		X		X	
Blood sample for hematology	X	X				X		X	
Blood sample for chemistry	X	X				X		X	

This document is confidential. It contains proprietary information of Supernus Pharmaceuticals, Inc. Any viewing or disclosure of such information that is not authorized in writing by the Sponsor is strictly prohibited. Such information may be used solely for the purpose of reviewing or performing this study.

Study Period	Screening	Evaluation Period							Safety/ Follow-Up (FPC ^a)

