- The follow-up assessments will be performed through a safety follow-up phone call. The safety follow-up phone call will occur approximately 5 days after the last administration of SM.
- AEs reported during screening will be recorded as part of the subject's medical history.
- A complete physical examination will be performed at screening and baseline visits; a brief physical examination will be performed at EOS/ET.
- Vital signs measurements include orthostatic blood pressure/pulse rate, respiratory rate, and oral temperature. Orthostatic blood pressure and pulse rate should be measured after the subject has been sitting for 5 minutes and again within 3 minutes of subject standing.
- ECGs should be performed prior to blood draws.
- Serology tests include human immunodeficiency 1/2 antigen/antibody, hepatitis B surface antigen, and hepatitis C virus antibody.
- A standard urine drug screen will be performed at screening and point-of-care urine drug screen together with the breathalyzer will be performed at baseline (Day 1) and all post-baseline clinic visits (days 4, 7, and 10).
- On days 2, 3, 5, 6, 8, and 9, the HAM-D₆ questionnaire will be administered remotely by telephone.
- SAEs will be captured from the time of ICF signing, and AEs will be captured following the first administration of SM and continue through the FPC.
- Seven total blood samples will be collected for measurement of BDNF concentrations: 3 pre-dose collections on days 1, 4 and 7; 3 post-dose collections 4 hours after SM administration on days 1, 4, and 7; and 1 collection on Day 10.
- Subjects will take their SM in the clinic.
- Subjects will receive a paper ADT adherence diary at screening and document the day of each dose of their ADT throughout the study. Subjects will bring their ADT adherence

diaries to each clinic visit for review of subject compliance.

m. ADT will not be provided by the Sponsor. Subject's ADT will have started and have been stable for at least 6 weeks prior to screening and will continue through the safety follow-up phone call.

Table 2: Detailed Schedule of Timed Assessments (Window)

Study Day	Clinic Visit Number	Location	Time ^a		HAM-D ₆ ^b	MADRS ^b	CGI-S	BDNF ^c
1	2	Clinic	Pre-dose		X (-60 min)	X (-60 min)	X (-60 min)	X (-60 min)
			1 hour					
			2 hours		X (±30 min)			
			4 hours		X (±30 min)	X (±30 min)		X (±30 min)
			8 hours		X (±30 min)			
2	–	Home	24 hours		X (±2 h) ^e			
3	–	Home	48 hours		X (±2 h) ^f			

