6.1.5 Visit 5 – End of Study (Day 10)

The assessments listed below will be conducted. See [Table 2](#) for details of efficacy assessments.

- Administer HAM-D₆, MADRS, and CGI-S (approximately 72 hours after the SM administration on Day 7)
- Perform a brief physical examination
- Record body weight
- Record vital signs (orthostatic blood pressure and pulse rate, respiratory rate, and oral temperature)
- Perform 12-lead ECG
- Collect blood samples for:
 - Hematology and serum chemistry (non-fasted sample allowed)
 - BDNF
- Collect urine sample for:
 - Urine pregnancy test (FOCP only)
 - Urinalysis
 - Drug and alcohol screen
- Administer safety assessments (C-SSRS [Since Last Visit Version], CADSS, and BPRS+ scales)
- Review AEs
- Review concomitant medications
- Review and collect ADT adherence diary

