8.3. Vital Signs

8.3.1. Absolute Value and Change from Baseline

The CFB in vital sign variables will be calculated for each post-baseline visit. The postural change in blood pressure and pulse rate from sitting to standing will be calculated for each visit. The analyses of vital signs will be summarized descriptively in the same manner as described in Section 8.2.1.

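### The protocol sets no time relative to dosing for orthostatic vital signs or ECG, and in the listed order the scheduled post-baseline sets fall about 72 h after a dose

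*Protocol*

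**What the plan says.** Dosing is in clinic: "Subjects will receive SM at the clinic on days 1, 4 and 7" (Protocol synopsis). Protocol 3.2.4 makes "Vital sign measurements including orthostatic blood pressure and pulse rate" a safety endpoint and lists ECG findings beside it.

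Protocol Table 1 has a row "Vital signs with orthostatic blood pressure and pulse rate" and a 12-lead ECG row. Each is marked once at screening and once on Days 1, 4, 7 and 10, with no clock time. Protocol Table 2, the timed schedule, visibly covers HAM-D6 (pre-dose, 2, 4 and 8 h), MADRS and BDNF (pre-dose and 4 h) and CGI-S (pre-dose). It shows no vital-sign or ECG entry.

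The Day 1 and Day 7 lists (6.1.2, 6.1.4) put both measures above the dosing item and do not repeat them in the visible items below it; the Day 7 entry reads "Record vital signs (orthostatic blood pressure and pulse rate, respiratory rate, and oral temperature". The visible Day 4 list (6.1.3) names neither measure, although Table 1 requires both. A Table 1 footnote adds "ECGs should be performed prior to blood draws". The Day 10 scales are given "approximately 72 hours after the SM administration on Day 7" (6.1.5).

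On earlier experience, Protocol 2.4 reports: "The most frequently reported TEAEs by healthy subjects included dizziness (postural dizziness and orthostatic hypotension", followed by other events.

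SAP 8.3.1 states "The postural change in blood pressure and pulse rate from sitting to standing will be calculated for each visit". SAP 8.3 and 8.5 also plan change-from-baseline, shift, notable vital-sign and QTcF-category summaries.

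**The concern.** An orthostatic reading or ECG describes the drug's effect only at the time since dose at which it is taken. The plan does not state that time, and its internal order points to the end of the 3-day dosing interval. By-visit tables with no postural drop and no QTcF change could then be taken as evidence that neither occurs after dosing, when no reading in that period had been scheduled.

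The opposite possibility also causes trouble. A site that takes the Day 7 set after dosing does not breach Table 1. The SAP pools sites (3.4) and analyses by nominal visit (3.10), so values near trough and values hours after a dose could be averaged in one Day 7 row with nothing to tell them apart.

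**Working it through.** **Inputs.** Dosing on Days 1, 4 and 7 (synopsis). Vital signs and ECG on Days 1, 4, 7 and 10 (Table 1). First BDNF sample on each dosing day taken pre-dose, within 60 minutes of dosing (6.7, Table 2). Baseline is the latest available value before the first dose (SAP Table 2), so the Day 1 set must be pre-dose to serve as baseline.

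**Plan's own figure.** Day 7 dose to Day 10: (10 − 7) × 24 = 72 h. This agrees with the interval in 6.1.5.

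**Same arithmetic for the other sets, if taken before that day's dose.** Day 4: (4 − 1) × 24 = 72 h. Day 7: (7 − 4) × 24 = 72 h.

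**How firmly the text fixes each set**

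| Post-baseline set | Vital signs | ECG |
|---|---|---|
| Day 4 | No visible timing; pre-dose only by analogy with Day 7 | Footnote plus pre-dose BDNF sample implies pre-dose |
| Day 7 | List order only | List order plus footnote |
| Day 10 | About 72 h by visit definition | About 72 h by visit definition |

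**Is list order evidence of time order?** Mostly.
- Day 10 lists the efficacy scales first, as the Table 2 note on Day 10 requires.
- The drug screen is listed before the efficacy scales, as 6.5 requires.
- Pre-dose scales stand above the dosing item and post-dose scales below it.

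The match is not strict. Day 1 lists eligibility review first, although it depends on scores obtained later that day. The 4 h BDNF sample is listed after the post-dose scales, which include an 8 h HAM-D6.

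**Where readings outside the schedule go in the SAP**
- By-visit summaries: unscheduled values are excluded and, for repeats, the first non-missing value is used (3.1 and 8.2.1, applied by 8.3.1 and 8.5.1). A post-dose repeat after a pre-dose reading would drop out.
- Worst post-baseline shift: unscheduled values count (8.2.2, applied by 8.3.2 and 8.5.2).
- Notable vital signs: unscheduled visits count (8.3.3).
- QTcF categories: any post-baseline value (8.5.3); whether this overrides the default exclusion in 3.1 is not stated.

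**What one systematic post-dose set could show (illustration).** Assume a true incidence of 5%. The chance of at least one event is 1 − 0.95^50 = 92% with 50 subjects and 1 − 0.95^40 = 87% with 40. With no events, the one-sided 95% upper bound is 1 − 0.05^(1/50) = 5.8% or 1 − 0.05^(1/40) = 7.2%. The incidence is assumed; the documents give none.

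**The case against.** The strongest reply is that pre-dose timing is inferred. Neither document calls the visit lists chronological, and for Day 7 vital signs list order is the only evidence. That stands. The firm finding is that timing is unspecified; the 72 h result is conditional on the listed order.

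Second, the visible text is incomplete. The Day 4 list also lacks weight, urine tests and pre-dose scales, which suggests a block lost in PDF reading. There are redacted lines after dosing on Days 4 and 7, and Table 2 may hide a column. The context points to PK sampling, but this cannot be confirmed. So the point does not rest on Day 4, and the claim is limited to what is visible.

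Third, a reader might infer that these endpoints cannot detect post-dose effects at all, or that every SAP table describes trough. The documents do not support either inference. Extra vital signs and ECGs are allowed at the investigator's discretion (7.4.2, 7.4.4). An early-termination visit can fall sooner after a dose (4.4). Unscheduled values enter the worst-value shift and notable vital-sign analyses. Adverse events are sought by specific questioning (7.2.5). These routes depend on symptoms, judgement or withdrawal, so they do not replace a scheduled reading.

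Fourth, the prior evidence is limited. The orthostatic events were in healthy subjects; most events were mild, none was severe and all resolved. The list for treatment-resistant depression names dizziness but not orthostatic hypotension. No onset time is given and no ECG effect is named. Phase 1 may already have characterised acute effects, which cannot be judged from these documents. This lowers the urgency but does not settle what this trial's own safety tables mean.

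**Conclusion.** The point holds in a conditional form. Timing relative to dose is not set for two safety endpoints. If the listed order is followed, all three scheduled post-baseline sets fall about 72 h after the previous dose, and no visible text assures a systematic reading in the hours after any of the three doses. If it is not followed, the by-visit rows may mix trough and acute values. Either way, the tables cannot be interpreted without time since dose.

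This rests on list order for Day 7, on the blood-draw footnote for ECG, and on the redacted text holding no timed vital signs or ECG. A reader might go further and infer that almost no drug remains at 72 h. The half-life and time of peak are not visible, so no residual-exposure figure is offered and the conclusion does not need one.

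**What to change.** In the protocol:
1. State in Table 1 or Table 2 the time relative to dose for every vital-sign set and ECG. Keep Day 1 pre-dose as baseline and Day 10 as the 72 h value.
2. Time the Day 7 vital-sign set and ECG to a post-dose clock time that Table 2 already uses, with the hour chosen by the sponsor from its own PK data.
3. Reword the ECG footnote so that the ECG precedes the blood draw at the same time point. As written, a post-dose ECG would follow the pre-dose BDNF sample and breach it.
4. Reconcile Table 1 with the Day 4 list in 6.1.3, unless the full document already lists the measures there.

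In SAP 8.3 and 8.5, label results by time since dose, and show early-termination readings with their own time since dose.

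The cost is small because subjects are already in clinic for 8 h ratings. The Day 7 trough vital-sign and ECG values are given up. Alternatively, the pre-dose vital signs can be kept and one brief repeat set added; it must then be a scheduled time point of its own, or the first-value rule in the SAP would drop it.

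If the schedule stays as it is and sites follow the listed order, label the by-visit tables as about 72 h post-dose and state that they do not systematically assess acute orthostatic or QTcF effects. That needs only labels and a sentence.

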6.1.5 Visit 5 – End of Study (Day 10)

The assessments listed below will be conducted. See [Table 2](#) for details of efficacy assessments.

- Administer HAM-D₆, MADRS, and CGI-S (approximately 72 hours after the SM administration on Day 7)
- Perform a brief physical examination
- Record body weight
- Record vital signs (orthostatic blood pressure and pulse rate, respiratory rate, and oral temperature)
- Perform 12-lead ECG
- Collect blood samples for:
 - Hematology and serum chemistry (non-fasted sample allowed)
 - BDNF
- Collect urine sample for:
 - Urine pregnancy test (FOCP only)
 - Urinalysis
 - Drug and alcohol screen
- Administer safety assessments (C-SSRS [Since Last Visit Version], CADSS, and BPRS+ scales)
- Review AEs
- Review concomitant medications
- Review and collect ADT adherence diary

6.2 Home Evaluations

On days 2, 3, 5, 6, 8, and 9, subjects will receive a telephone call for safety and efficacy assessments. Subjects will continue to take their ADT.

6.2.1 Days 2, 3, 5, 6, 8 and 9

The following assessments will be conducted remotely by telephone:

- Review AEs
- Review concomitant medications
- Confirm compliance and remind subject to complete the ADT adherence diary
- Administer HAM-D₆ remotely approximately 24 and 48 hours (± 2 hours) after each administration of SM on days 1, 4, and 7 as detailed in [Table 2](#)

6.3 Safety Follow-Up Phone Call (Day 12)

Subjects who complete EOS/Study Day 10 will receive a safety follow-up phone call approximately 5 days (+2 days) after the administration of SM on Day 7.

The following assessments will be conducted:

- Administer safety assessments (C-SSRS [Since Last Visit Version], CADSS, and BPRS+ scales)
- Review AEs
- Review concomitant medications

6.4 Unscheduled Visits

At the discretion of the investigator throughout the study, unscheduled visits may be conducted to perform or repeat assessments, including to record an ECG, measure vital signs (orthostatic blood pressure/pulse rate) or body weight, draw a blood sample for hematology and/or serum chemistry or serum pregnancy test (FOCP) or alcohol drug screen, obtain urine sample for urine pregnancy test and/or drug screen, administer the C-SSRS, and/or perform a physical examination. AEs and concomitant medications should be reviewed and recorded at all unscheduled visits.

